
Concomitant Medications:
 
To minimize nausea, unless contraindicated, all patients should receive 5-hydroxytryptamine (5-HT3) antagonists (e.g., ondansetron 8 mg or equivalent) starting on Day 1 before the first dose of selinexor and continued 2-3 times daily, as needed. Alternative anti-emetic agents should be used if the patient does not tolerate 5-HT3 antagonists. Additional anti-nausea and anti-anorexia agents may be given as needed (per National Comprehensive Cancer Network® [NCCN] Clinical Practice Guidelines® for Antiemesis and NCCN Clinical Practice Guidelines® for Palliative Care). Patients will also receive therapy as needed to mitigate selinexor side effects, as part of best supportive care. Blood product transfusions, antimicrobials, and (as appropriate) growth factors including granulocyte colony-stimulating factors for neutropenia, erythropoietins for anemia, and/or platelet-stimulating factors for thrombocytopenia are also permitted.
 
Patients may continue their baseline medication(s). Medications to treat concomitant diseases such as diabetes, hypertension, etc., are allowed. Patients will also receive concomitant medications that are medically necessary as standard care to treat symptoms, AEs and intercurrent illnesses. Patients may receive red blood cell or platelet transfusions, or blood growth factors, if clinically indicated, per institutional guidelines.
 
Concurrent therapy with any other approved or investigational anti-cancer therapy is not allowed. Other investigational agents should not be used during the study.
		

Study Numbers:
 
Approximately 210 patients will be enrolled overall, including 79 patients (with quad-refractory MM and penta-refractory MM) in Part 1 and ~130 patients (with penta-refractory MM only) in Part 2 (to achieve the target population size of N = 122 for the primary efficacy analysis).
		

Study Duration:
 
The enrollment period for this study is expected to be approximately 24 months. There is no maximum treatment duration for the study or pre-defined number of treatment cycles
		

Sponsor: Karyopharm Therapeutics Inc.	Investigational Product: Selinexor (KPT-330)	Developmental Phase: Phase 2b

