1.6. DATABASE LOCK

The primary analysis will be performed after all patients have completed the Cycle 2 MM Assessments, and will include a formal snapshot of database and analyses of efficacy, safety, and PK data. A clinical study report (CSR) will be prepared after the primary analysis. The data cut date for IRC-based MM response assessment may be later than the data cut date for other data points. All data points presented to IRC members for their assessment have been source verified.

At the time of the database snapshot for the primary analysis, the median DOR estimate may not be estimable with limited follow-up time. Therefore, an efficacy update on ORR and DOR among the Part 2 patients with penta-refractory MM will be provided before the submission of the New Drug Application (NDA) package.

The final analysis will be performed at the end of the study after all patients have completed the 12-month follow-up period (i.e., when the last patient has expired, been followed for 12 months after last dose of study treatment, been lost to follow-up, or has withdrawn consent, whichever occurs first). There will be a formal database lock and analyses of efficacy and safety data. A final CSR will be prepared summarizing the results from the full analysis.

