4. EFFICACY

Patient response at each time point will be assessed centrally by an IRC according to the IMWG response criteria (*Kumar 2016*) for MM. Unless otherwise specified, MM response assessment refers to assessment determined by IRC. The primary endpoint (ORR) is based on these IRC assessed responses in the mITT population.

Documentation of response requires two consecutive readings of the applicable disease parameter (serum M-protein, urine M-protein, serum FLC, or quantitative immunoglobulin level), performed at any time with no minimum interval required between the two readings. The date of response or PD will be assigned to the earlier date of the two independent samples, unless PD is based on an unambiguous criterion such as a new plasmacytoma lesion.

If a patient had one PD assessment but was not subsequently confirmed, unless IRC considers the progression assessment unambiguous, it is not considered a PD (*Kumar 2016*).

Unless otherwise specified, efficacy analyses will use the mITT population. Analyses for the primary efficacy endpoint of ORR and the key secondary efficacy endpoints of DOR, CBR, and duration of clinical benefit will be repeated in the other efficacy populations and additional analysis populations. If relevant, selected efficacy analyses for other efficacy endpoints will be repeated in selected additional analysis populations.

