4.2.7. Overall Survival (OS)

4.2.7.1. Definition

OS is defined as the duration from start of study treatment to death from any cause. If death event did not occur during the follow-up period, the patient is censored at the date of discontinuation from the study, or date of last participating visit (e.g., a telephone contact with patient status being alive), or database cut date, whichever is earlier.

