4.2.7.2. Analysis Methods

The proportion of patients with death event and the 2-sided, exact 95% CI will be calculated using the mITT population. Median OS time with 95% CI will be estimated based on the Kaplan-Meier method. The Kaplan-Meier curve for OS will be provided.

The following supportive OS analyses will be conducted:

- Using the BCLPD-ref, CLPD-ref, BCPD-ref, CPD-ref populations respectively
- Using the all penta-ref, high-risk, EE, PP, Part 1 – Quad, Part 1 – Penta, respectively, if sufficient data exist

- The same as in primary OS analysis except additional censoring at the start date of a new MM treatment
- In patients with R-ISS for MM stage I, II, and III respectively, if sufficient data exist
- In US vs. non-US patients, if sufficient data exist
- In FLC MM vs. non-FLC MM patients, if sufficient data exist
- In patients with a best response of confirmed PR or better
- In patients with a best response of confirmed MR or better
- In patients with a best response of confirmed MR
- In patients with a best response of SD or worse (including patients whose disease is not evaluable)

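### Overall survival by best response runs from first dose with no landmark, so the groups cannot fairly be read against each other; the exact interval on the death proportion has no time point

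*SAP*

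**What the plan says.** SAP 4.2.7.1 fixes the time origin: "OS is defined as the duration from start of study treatment to death from any cause". Among the supportive OS analyses in 4.2.7.2 are four by best response: PR or better ("In patients with a best response of confirmed PR or better"), MR or better, MR alone, and "In patients with a best response of SD or worse (including patients whose disease is not evaluable". No other origin, landmark or time-dependent model appears in that section, which is not redacted.

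Under SAP 4.1.1 a response can be reached during or after treatment, up to progression or a new myeloma therapy. Assessments are every 28 days (note to SAP 4.2.5.2), and the schedule adds free light chain at Day 15 of Cycles 1 and 2. Confirmation needs two readings, "performed at any time with no minimum interval required between the two readings" (SAP 4), so it adds little waiting time.

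The same section opens with a second item: "The proportion of patients with death event and the 2-sided, exact 95% CI will be calculated using the mITT population". No month is named. On timing, SAP 1.6 says "The primary analysis will be performed after all patients have completed the Cycle 2 MM Assessments" and later "The final analysis will be performed at the end of the study after all patients have completed the 12-month follow-up period". The Protocol Synopsis (Study Duration) says "The enrollment period for this study is expected to be approximately 24 months".

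**The concern.** **Response groups.** The groups are formed by an event after time zero. Responders carry a stretch of guaranteed survival; patients who die before they can be assessed go to SD or worse by rule. This is guarantee-time bias, and its direction is known. With the four curves in one report, readers will compare them, and a single-arm trial has no control group to show how much of the gap the grouping rule created.

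**Death proportion.** A binomial interval treats each patient as having the same chance to show the event. At the primary snapshot, follow-up ranges from about Cycle 2 to the length of accrual, and patients censored alive count as survivors. The interval therefore does not estimate the risk of death at any stated time.

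**Working it through.** The plan states no OS figure, so there is none to reproduce.

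**Inputs from the documents.** Part 1 penta-refractory: ORR 6/30 = 20%, CBR 12/30 = 40%, hence MR 20% (Protocol Table 3). Target N = 122 (Synopsis, Study Numbers). Visits every 28 days.

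**Assumptions.** Exponential OS with median 4, 6, 9 or 12 months; response has no effect on survival; first response at Day 29, 57 or 85 (28, 56, 84 days after first dose, or 0.92, 1.84, 2.76 months).

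**(a) Response groups**

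Let m = median/ln 2 be mean OS, p the responder share and τ the mean time to response among observed responders. Exponential survival has no memory, so with follow-up to death:

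- mean OS in responders: R = m + τ
- mean OS in the others: O = (m − pR)/(1 − p)
- apparent death-rate ratio, responders to others: (1/R)/(1/O) = O/R

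Worked case: median 9 months, first responses split 50/30/20% over Days 29/57/85.

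- m = 9/0.693 = 12.98.
- Survival to the three visits is 0.932, 0.868 and 0.809, so the weights are 0.466, 0.260 and 0.162 (sum 0.888).
- τ = (0.466×0.92 + 0.260×1.84 + 0.162×2.76)/0.888 = 1.53.
- R = 14.51; O = (12.98 − 0.2×14.51)/0.8 = 12.60; ratio = 0.87.
- Median OS is 10.5 against 8.6 months.

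All scenarios, responders against everyone else; the true ratio is 1. Simulation gives the same values within 0.01.

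| First response | Median 4 | 6 | 9 | 12 months |
|---|---|---|---|---|
| All at Day 29 | 0.83 | 0.88 | 0.92 | 0.94 |
| 50/30/20% at Days 29/57/85 | 0.75 | 0.81 | 0.87 | 0.90 |
| All at Day 85 | 0.60 | 0.70 | 0.78 | 0.83 |

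The SAP's lowest group excludes MR. Adding a 20% MR rate with the same timing makes the removed share 0.4. In the worked case O = (12.98 − 0.4×14.51)/0.6 = 11.97, the ratio is 0.82 and the medians are 10.5 against 7.9 months. Over all scenarios the ratio then runs from 0.46 to 0.92.

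A separate simulation used medians of 5, 8 and 12 months, latent PR and MR rates of 25% each, and responses spread over up to six cycles. For PR or better against SD or worse it gave 6.6–8.0 against 3.4–3.7, 9.7–11.2 against 5.5–6.5, and 13.7–15.2 against 9.3–10.5 months: a spurious gap of about 3 to 6 months.

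From a Day 85 landmark, the group medians agree within 0.1 month in every scenario. The share dying before it is 1 − 2^(−2.76/median) = 38%, 27%, 19% and 15% at medians of 4, 6, 9 and 12 months.

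**(b) Death proportion**

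Take median OS 9 months (λ = 0.0770 per month), uniform accrual over A months and at least 1 month of follow-up. The expected proportion dead at the snapshot is

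P = 1 − [exp(−λ) − exp(−λ(1 + A))]/(λA).

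For A = 12: 1 − (0.926 − 0.367)/0.924 = 40%. The true risks are 1 − 2^(−6/9) = 37% at 6 months and 1 − 2^(−12/9) = 60% at 12 months. Coverage below is the binomial probability, with N = 122 and P, of a death count whose exact 95% interval contains the stated risk.

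| Accrual | Proportion dead | Covers 6-month risk | Covers 12-month risk |
|---|---|---|---|
| 12 months | 40% | 93% | 0.5% |
| 18 months | 50% | 21% | 39% |
| 24 months | 58% | 0.5% | 92% |

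At the final analysis each patient is followed to 12 months after last dose, so accrual drops out. With assumed median treatment of 2 to 4 months, the proportion is 68–73% with no withdrawal and 58–61% if 30% withdraw in the first year.

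**The case against.** The strongest reply is that the bias belongs to a comparison the SAP does not plan. SAP 4.2.7.2 pairs other subgroups explicitly (US against non-US, FLC against non-FLC), but the response bullets stand alone and overlap. SAP 2.1 calls Kaplan-Meier summaries descriptive, and Protocol 13.1.1 provides hypothesis testing only for the primary endpoint. All of that stands and limits the weight. It does not stop the curves being read together, and nothing visible warns against it.

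The sizes rest on assumed survival and response timing. That also stands; the direction does not depend on them. Comparing responders with everyone else matches no pair in the SAP, but using the SAP's own groups widens the gap.

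In Part 1, 7 of 30 penta-refractory patients were not evaluable, which is 7 of the 18 (6 SD + 5 PD + 7 NE) who would be SD or worse. Table 3 gives no reasons, so this shows how large the not-evaluable share can be, not how many died early.

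On the death proportion, the SAP never calls it a 6- or 12-month risk, and the Kaplan-Meier median and curve beside it already handle censoring. Part 2's own accrual length is not stated; the 24 months is for the study. These are fair, and they make this the lesser point. The interval still has no stated target.

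**Conclusion.** Both points hold, at modest weight. Read against each other, the first-dose curves by best response favour responders even with no true effect. Under the stated assumptions the apparent death-rate ratio is 0.60–0.94 against all other patients, or 0.46–0.92 against SD or worse as the SAP defines it. The exact interval on the death proportion estimates no defined survival risk; at the primary snapshot, with a 9-month median, the proportion moves from 40% to 58% as accrual goes from 12 to 24 months.

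These sizes depend on exponential survival, the assumed medians and the assumed response times. SAP 4.3 is redacted, so a landmark rule there cannot be excluded. The primary ORR test and the mITT Kaplan-Meier OS analysis are untouched.

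**What to change.** In SAP 4.2.7.2, run the response-group OS summaries from a pre-specified landmark, for example Cycle 4 Day 1: include patients alive and in follow-up, classify them by response status on that day, and count OS from then. A model with response as a time-dependent covariate is an alternative. If the first-dose curves are kept, add a sentence that they are descriptive and must not be compared across groups; that is the minimum change.

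Replace the exact interval on the death proportion with Kaplan-Meier OS at 6 and 12 months and 95% confidence intervals, and give the number of deaths as a plain count.

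The cost is SAP wording and programming, with no new data. The landmark drops patients who die or are censored before it (deaths alone 15–38% across the assumed medians) and counts later responders as non-responders. It also answers a somewhat different question from OS by best response. An earlier landmark keeps more patients but misclassifies more late responders.

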4.2.8. Quality of life (QoL)

4.2.8.1. Definition

Health-related QoL and potential for improvement over the course of the study will be assessed using the Functional Assessment of Cancer Therapy – Multiple Myeloma (FACT-MM) patient-reported outcome questionnaire that is specifically relevant to MM. This instrument combines the general version of the FACT (FACT-G) with a MM-specific subscale (14 items). The subscales for the FACT-G are Physical Well-Being (7 items), Social/Family Well-Being (7 items), Emotional Well-Being (6 items), and Functional Well-Being (7 items). The trial outcomes index (TOI; total of 41 items) will be the primary measurement of interest, comprised of the Physical and Functional subscales plus the MM-specific subscale. Each item is rated on a 5-point Likert scale, ranging from 0 (“Not at all”) to 4 (“Very much”), therefore the TOI has a score ranging from 0 to 120. The QoL assessment will be performed at Baseline (prior to first dose of study treatment), Day 1 of each cycle on or after the second, and at the Final visit.

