
Efficacy Evaluation:
 
The primary statistical analysis of efficacy will be performed on ORR (proportion of patients who achieve sCR, CR, VGPR, or PR) using the modified intent-to-treat (mITT) population, defined as Part 2 patients with penta-refractory MM who met all eligibility criteria (or did not meet all eligibility criteria but received waiver from Sponsor to participate in the study), and received at least 1 dose of study treatment (partial or complete). The primary analysis will be performed on the Part 2 patients with penta-refractory MM only.
 
A per-protocol (PP) population will consist of all patients in the mITT population who meet the following criteria:
 

• Have selinexor compliance <math>\geq 70\%</math>,

• Have at least 1 adequate post-baseline response assessment unless died or withdrew from study before that.

• No major protocol violations that would compromise the assessment of efficacy. The list of major protocol violations that affect statistical analysis will be finalized before database lock.

 
The PP population will be used for supportive inferences concerning efficacy.
 
Secondary CCI endpoints will be assessed using the mITT population and the PP population. Time-to-event endpoints (including DOR) will be assessed using Kaplan-Meier methods.
 
Quality of life (QoL) will be assessed using the Functional Assessment of Cancer Therapy with MM-specific subscale (FACT-MM). The trial outcomes index (TOI) will be the primary measurement of interest, comprised of the physical and functional subscales plus the MM-specific subscale.
 
Safety Evaluation:
 
Safety analyses will be performed on the overall population of patients who received any amount of study treatment, presented overall and by study part.
		

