QoL will be assessed using the Functional Assessment of Cancer Therapy-Multiple Myeloma (FACT-MM). This instrument combines the General version of the FACT (FACT-G) with a MM-specific subscale (14 items). The subscales for the FACT-G are Physical Well-Being (7 items), Social/Family Well-Being (7 items), Emotional Well-Being (6 items), and Functional Well-Being (7 items). The trial outcomes index (TOI; total of 41 items) will be the primary measurement of interest, comprised of the Physical and Functional subscales plus the MM-specific subscale. Each item is rated on a 5-point Likert scale, ranging from 0 (“Not at all”) to 4 (“Very much”), therefore the TOI has a score ranging from 0 to 120. The QoL assessment will be performed at Baseline (prior to first dose of study treatment), Day 1 of each cycle on or after the second, and at the Final visit. The QoL analysis will be based on changes in the total TOI score from Baseline using paired T-tests. A secondary analysis of QoL will be performed in a similar manner using the total of all subscales. All 5 individual subscale total scores will be summarized over time using descriptive statistics.

Additionally, the following analyses of safety and tolerability secondary endpoints will be performed on the overall population of patients who received any amount of study treatment, presented overall and by study part.

- Safety and tolerability using National Cancer Institute (NCI) Common Terminology Criteria for Adverse Events (CTCAE), v 4.03.
- Describe the PK properties of selinexor in this patient population (Part 1 only).

CCI [REDACTED]

[REDACTED]

[REDACTED]

[REDACTED]

[REDACTED]

[REDACTED]

[REDACTED]

[REDACTED]

[REDACTED]

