4.2.8.2. Analysis Methods

The primary analysis for QoL will be based on the change from baseline on the TOI score at each assessment time point, which will be summarized using descriptive statistics including mean, standard deviation, median, minimum, and maximum. The total score considering all 5 subscales as well as the 5 individual subscale sums of scores will be summarized similarly. The same analysis windows as in Table 2-1 will be used with the only exception that C1D15 is not considered as the questionnaire was not scheduled to administer during that visit.

The following supportive analyses will be conducted:

- In patients with a best response of confirmed PR or better
- In patients with a best response of confirmed MR or better

4.3.

CCI

CCI [REDACTED]
[REDACTED]

[REDACTED]
[REDACTED]
[REDACTED]

[REDACTED] [REDACTED]

[REDACTED]
[REDACTED]
[REDACTED]
[REDACTED]

- [REDACTED]
[REDACTED]
[REDACTED]

- [REDACTED]

- [REDACTED]

- [REDACTED]

[REDACTED]

- [REDACTED]

- [REDACTED]

[REDACTED]
[REDACTED]

[REDACTED]
[REDACTED]

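### The TOI's printed item count (41) and range (0 to 120) contradict its named subscales, which give 28 items and 0 to 112

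*SAP*

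**What the plan says.** SAP section 4.2.8.1 and protocol section 13.3.4 describe the FACT-MM in near-identical text. They list five subscales: Physical (7 items), Social/Family (7), Emotional (6), Functional (7) and myeloma-specific (14). Each item is scored from 0 to 4.

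Both then define the trial outcomes index: "The trial outcomes index (TOI; total of 41 items) will be the primary measurement of interest, comprised of the Physical and Functional subscales", with the myeloma-specific subscale added. On the range, both say "therefore the TOI has a score ranging from 0 to 120". The protocol synopsis, under Efficacy Evaluation, names the same three components without a count or range: "comprised of the physical and functional subscales plus the MM-specific subscale".

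The TOI leads the quality-of-life analysis. SAP section 4.2.8.2 states: "The primary analysis for QoL will be based on the change from baseline on the TOI score at each assessment time point". The five-subscale total is a separate analysis in both documents. The SAP says "The total score considering all 5 subscales as well as the 5 individual subscale sums of scores will be summarized similarly", and protocol section 13.3.4 says "A secondary analysis of QoL will be performed in a similar manner using the total of all subscales".

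**The concern.** One short definition describes the same score in three incompatible ways: by its components, by its number of items and by its range. The printed count and range also disagree with each other, because 41 items scored 0 to 4 would run to 164, not 120.

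The definition is the specification from which the score is programmed and checked. A programmer who works from the count would build the full FACT-MM total and label it TOI. The SAP's lead quality-of-life variable and the separately planned total would then be the same number, and the Social/Family and Emotional items, which the definition leaves out, would enter the TOI.

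Even with correct code, the printed figures are poor checks. A range check at 0 to 120 would accept impossible TOI values from 113 to 120, and an item check at 41 would reject a correctly built score. Neither reference list cites a scoring source for the FACT-MM that would settle the matter.

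**Working it through.** **Inputs** (SAP 4.2.8.1; the same in protocol 13.3.4)

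| Subscale | Items | Named as part of the TOI |
|---|---|---|
| Physical | 7 | yes |
| Social/Family | 7 | no |
| Emotional | 6 | no |
| Functional | 7 | yes |
| Myeloma-specific | 14 | yes |

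Each item scores 0 to 4, so the maximum of any sum is the number of items × 4.

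**Trying to reproduce the printed figures**

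- *41 items.* All five subscales: 7 + 7 + 6 + 7 + 14 = 41. Maximum 41 × 4 = 164. So 41 can be reproduced, but only as the full FACT-MM.
- *Maximum of 120.* 120 / 4 = 30 items. The 31 non-empty combinations of the five subscales give only 6, 7, 13, 14, 20, 21, 27, 28, 34, 35 or 41 items. The corresponding maxima are 24, 28, 52, 56, 80, 84, 108, 112, 136, 140 and 164. Neither 30 items nor a maximum of 120 can occur. The reason is that four of the sizes are multiples of 7 and the fifth is 6, so every sum is a multiple of 7 or 6 more than one, and 30 is neither. For the same reason 41 = 35 + 6 occurs only when all five subscales are included.
- *FACT-G alone*, as a further candidate: 41 − 14 = 27 items, maximum 27 × 4 = 108. This does not match either.

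**The TOI as composed**

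7 + 7 + 14 = 28 items; maximum 28 × 4 = 112.

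| Basis | Items | Range |
|---|---|---|
| Named components | 28 | 0 to 112 |
| Printed item count | 41 | 0 to 164 |
| Printed range | 30 (not attainable) | 0 to 120 |

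**Consequence if 41 items were coded**

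- Items from outside the TOI: 7 + 6 = 13, and 13 / 41 = 31.7%.
- Points from outside the TOI: 13 × 4 = 52 of 164.
- The TOI would equal the five-subscale total for every patient at every visit.

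**Consequence if the three named subscales are summed**

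None. The visible analysis text summarises change from baseline and applies no threshold, responder cut-off or rescaling that uses the printed maximum.

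**The case against.** The strongest reply is that this is an editorial slip. The synopsis, protocol 13.3.4 and SAP 4.2.8.1 all name the same three subscales, so the intended score is clear. To code 41 items a programmer would have to ignore the components named in the same sentence and add two subscales that the TOI definition does not mention. The SAP already separates the TOI from the five-subscale total, and two identical tables would be noticed on review. Nothing shows that the score was or would be coded that way, and the wrong maximum feeds no planned calculation. Quality of life is one secondary endpoint among several in a single-arm study whose primary endpoint is IRC-assessed response.

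All of this stands, and it limits the weight of the point. It does not remove the error. The wrong figures sit in the operative definition of the SAP's lead quality-of-life variable, in both documents, and nothing in the visible text corrects them. The amendment to protocol version 6.0 updated statistical language for consistency with the SAP, yet both figures remain in the current protocol.

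Two further remarks are fair. Protocol 13.3.4 also plans paired t-tests on the change in TOI, whereas the SAP only describes it; these tests too are unaffected if the named subscales are summed. And the figures of 28 and 112 rest on the subscale sizes printed in the documents. The printed 41 agrees with those sizes, since they add up to it, but the instrument's own scoring instructions are not included.

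**Conclusion.** The point holds. On the documents' own subscale sizes and item scoring, the TOI has 28 items and a range of 0 to 112, not 41 items and 0 to 120. The count is 13 too high (41 − 28) and the maximum 8 points too high (120 − 112). The two printed figures are also incompatible with each other.

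The effect on results is conditional. It is zero if the three named subscales are summed. If the printed count is coded, the TOI and the total score coincide and about a third of the items come from subscales outside the definition. The correction should be made, but nothing in the primary response-rate analysis depends on it.

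The conclusion assumes only that the printed subscale sizes (7, 7, 6, 7, 14) and the 0 to 4 item scoring are correct.

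**What to change.** In protocol section 13.3.4 and SAP section 4.2.8.1, replace the count and range with a statement to this effect: the TOI is the sum of Physical (7), Functional (7) and myeloma-specific (14) items, 28 items in all, range 0 to 112; the FACT-MM total is the sum of all five subscales, 41 items, range 0 to 164, and is analysed separately.

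Then confirm that the scoring program sums only the three named subscales for the TOI and that any range check uses 112. It is sensible to compare the subscale sizes with the instrument's scoring instructions at the same time.

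The cost is one sentence in each document and one check of the program. No new data or analysis is needed.
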